4.5.4 Sensitivity Analyses

Sensitivity analyses will be performed to evaluate the robustness of the primary analysis results.

- **Parametric Model.** The primary efficacy endpoint will be re-analyzed using a negative binomial regression model, using the same covariates as specified for the primary analysis with Poisson regression. All other elements of the analysis will remain the same as in the primary analysis.

The following analyses will be performed to assess the sensitivity of results to missing data assumptions:

- **Missing Data Assumptions.** The primary endpoint (incidence of asthma exacerbations) and all secondary efficacy endpoints (except for time to first asthma exacerbation) found to be significant for a given MSTT1041A arm will be re-analyzed assuming that missing data is missing not at random, rather than missing at random (MAR), via tipping point sensitivity analyses implemented using multiple imputation. In general, imputation models will account for the same baseline covariates as used in the earlier described analysis of the endpoint and post-baseline outcome data when possible. Multiple imputed datasets will be grouped by a range of missing data assumptions and analyzed according to the same analysis models specified in Section 4.5, and the results will be combined for each assumption using Rubin's rules (Barnard and Rubin 1999). These analyses will be implemented as follows:
 - For continuous secondary endpoints that assess absolute changes from baseline to Week 54 (e.g., for pre-bronchodilator FEV1), imputation under the MAR assumption will be used to generate multiple datasets with imputed values. It will be assumed that the pattern of missing data in the outcome to be analyzed is monotone. In the event that the missing data do not follow a monotone pattern, multiple imputation using Markov chain Monte Carlo methods will be used to partially impute data under MAR, thereby converting the dataset to a monotone missing pattern. After imputation to achieve a monotone missing pattern, the remaining missing values will be imputed using a regression-based approach in a sequential manner with the use of univariate models, separately in each treatment group. For each visit, a regression model based on all patients who have observations (imputed or observed) available up to and including this visit will be fitted and used to impute missing values at this visit. All regression-based imputation models will include the baseline covariates described in Section 4.5 and prior observed or imputed outcomes.
 - Tipping-point analysis will be implemented by adding (or subtracting) a constant Δ to the post-dropout MAR imputed values; a separate Δ will be applied to each treatment arm (each MSTT1041A dose level and placebo). A range of Δ will be used to adjust post-dropout imputed values in the MSTT1041A and placebo arms independently based on a grid of Δ adjustments. For each endpoint, the size of the Δ will be chosen on the basis of the estimated treatment effect for a given MSTT1041A arm compared with placebo from the analyses specified in Section 4.5.2. The range will be chosen to include cases in which dropouts from the MSTT1041A arm have worse outcomes than dropouts from the placebo arm. For each endpoint, the resulting point estimates of treatment effect and corresponding p-values under each pair of Δ for each MSTT1041A arm and placebo comparison will be tabulated.
 - For the primary endpoint (incidence of asthma exacerbations), tipping point analysis via multiple imputation of event counts assuming a range of Δ will be performed. Event counts will be imputed at the patient level for the unobserved period between the last study visit and Week 54 for patients who discontinued study assessments

early. An event count corresponding to each unobserved period will be imputed by first fitting a negative binomial generalized linear model to the observed data and sampling from the posterior distribution of the model parameter estimates. These sampled parameter estimates along with the patient-specific observed covariate values, observed exacerbation counts, and length of unobserved interval will be used in conjunction with a random number generator to impute an event count for the unobserved time period, which is added to the observed event count (Keene et al. 2014). These augmented datasets will be analyzed according to the model described in Section 4.5.1 and the results combined using Rubin's rules.

- In the tipping point sensitivity analysis, the underlying event rate used to impute unobserved event counts for a given arm will be adjusted via a multiplier delta; a separate delta will be applied to each arm. A range of delta values will be used to adjust the underlying event rate used for imputation in the MSTT1041A and placebo arms independently based on a grid of delta adjustments. The delta values will be chosen on the basis of the treatment effect (rate ratio) observed for a given MSTT1041A arm compared with placebo from the analyses described in Section 4.5.1. The range of delta values will include cases where dropouts from the MSTT1041A arm are assumed to have worse outcomes than dropouts from the placebo arm. For each endpoint, the resulting point estimates of treatment effect and corresponding p-values under each pair of deltas for each MSTT1041A and placebo comparison will be tabulated.

Also, for the secondary endpoint (absolute change from baseline in FEV₁), a cumulative responder plot which displays, by treatment arm, the proportion of patients who achieve each specified absolute change in pre-bronchodilator FEV₁ from baseline at Week 54 for a range of possible FEV₁ changes will be provided. For this plot, patients with missing Week 54 data will be assumed to be non-responders.

4.5.5 Subgroup Analyses

Exploratory subgroup analyses of the primary efficacy endpoint will be performed to evaluate the consistency of the primary analysis results across pre-specified subgroups defined by demographic and baseline characteristics. The following subgroups will be analyzed with respect to the primary efficacy endpoint (incidence of asthma exacerbations) and for the secondary efficacy endpoint (absolute change in pre-bronchodilator FEV₁ from randomization at Week 54):

- Age (18 to <50 years, 50 to <65 years, ≥65 years)
- Sex (male, female)
- Baseline ICS total daily dose (<1000 µg, ≥1000 µg of fluticasone propionate or equivalent)
- Number of asthma exacerbations in the 12 months prior to study entry (1 event, 2 events, ≥3 events)
- Geographic region (North America, Latin America, Eastern Europe, Western Europe plus Rest of World)

Biomarker subgroup analyses are specified in Section 4.5.6.

A Poisson regression model similar to that specified for the primary analysis (Section 4.5.1) will be used for each subgroup analysis based on data subset for the patient subgroup of interest. Baseline covariates included in the primary analysis but no longer relevant given the subgroup of interest will be excluded from the model. A similar approach will be used for the secondary efficacy endpoint based on FEV₁. If convergence problems with the statistical models arise due to a small number of patients per subgroup, the analysis may be simplified by combining some of the subgroups or by excluding baseline stratification variables from the model. The estimated treatment effects (MSTT1041A vs. placebo) and corresponding 95% CIs from the models will be displayed graphically for each MSTT1041A dose level and each level of the subgroups specified.

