Eligible patients were randomized in a 1:1:1:1 ratio to receive MSTT1041A at one of three doses (70, 210, or 490 mg) or placebo. Enrollment caps were utilized to ensure adequate power for biomarker subgroup analysis based upon blood eosinophil status at visit 1 (≥ 300 , < 300 cells/ μ L). The randomization was conducted such that approximately 30 patients per arm will have eosinophil-high status and approximately 95 patients per arm will have eosinophil-low status. Study drug is administered as four SC abdominal injections at the randomization visit (Week 2), Week 6, and every 4 weeks thereafter through Week 50.

[figure not shown]
Safety and efficacy, as well as pharmacokinetic (PK) and pharmacodynamic (PD) measures, are assessed throughout the double-blind treatment period, as described in the protocol and detailed in the Schedule of Assessments (see [Appendix 2](#)). The primary efficacy endpoint is the incidence of asthma exacerbations during the 52-week double-blind treatment period (Week 2 through Week 54).

All patients will be followed for 20 weeks after the last dose of study treatment. The 20 weeks include 4 weeks after the final dose in the double-blind treatment period and 16 weeks in the safety follow-up period. Assessments for the safety follow-up period are detailed in the Schedule of Assessments (see [Appendix 2](#)).

All patients who discontinue study drug early during the double-blind treatment period are asked to continue with the study assessments in the double-blind treatment period and then complete the safety follow-up period. Patients who are unable or unwilling to continue with assessments in the double-blind treatment period complete an early termination visit and then enter the safety follow-up period.

The study design is depicted in [Figure 1](#).

Figure 1 Study Schema

ICS=inhaled corticosteroid; Q4W=every 4 weeks; SC=subcutaneous.

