2.2 DETERMINATION OF SAMPLE SIZE

A total of 502 patients were randomly allocated in a 1:1:1:1 ratio to receive one of three doses of MSTT1041A or placebo. This sample size provides approximately 80% power to detect a 40% reduction in the annualized asthma exacerbation rate (AER) between one MSTT1041A arm and the placebo arm, assuming 0.63 exacerbations per patient per year in the placebo arm, no Poisson over dispersion, a 15% dropout rate, and a two-sided significance level (α) of 0.05.

Enrollment caps are utilized to ensure adequate power for biomarker subgroup analysis based upon blood eosinophil status at visit 1. Approximately 30 eosinophil-high patients (≥ 300 cells/ μ L) per arm and approximately 95 eosinophil-low patients (< 300 cells/ μ L) per arm are randomly allocated. The sample size provides approximately 80% power to detect a 50% reduction in the annualized AER for the subgroup of eosinophil-high patients assuming 1.0 exacerbations per patient per year in the placebo arm, a 15% dropout rate, a two-sided significance level of 0.15, and 30 patients in each treatment arm having eosinophil-high status. The sample size also provides approximately 67% power to detect a 35% reduction in the annualized AER for the subgroup of eosinophil-low patients, assuming 0.5 exacerbations per patient per year in the placebo arm, no Poisson over dispersion, a 15% dropout rate, a two-sided significance level of 0.15, and 95 patients in each treatment arm having eosinophil-low status.

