- **Alternative Subgroups for Blood Eosinophils:** Patients will be categorized into blood eosinophil subgroups defined as ≥ 150 cells/ μL and < 150 cells/ μL at visit 1.
- **Alternative Subgroups for *IL1RL1* Genotype:** Patients will be categorized into one of three genotype subgroups: TT, CT, or CC.

Covariate adjustment for these analyses will follow the principles as described in Section 4.5. All other elements of the analysis will remain the same as in the primary analysis. If convergence problems with the statistical models arise due to a small number of patients per subgroup, the analysis may be simplified by excluding baseline stratification variables from the model. Point estimates for the treatment benefit (MSTT1041A vs. placebo) within each biomarker patient subgroup will be presented as defined above, along with associated 95% CIs and p-values.

Additional exploratory analyses that will be performed include:

- **Prognostic Effect:** The prognostic effect of blood eosinophils and *IL1RL1* genotype will be evaluated by assessing the relationship between baseline biomarker levels and the observed rate of protocol-defined exacerbations based on patients who received treatment with placebo.
- **Treatment by Biomarker Interaction:** This study was not designed to compare the reduction in asthma exacerbation rate associated with MSTT1041A treatment between the biomarker-high/genotype-positive and the biomarker-low/genotype-negative patient groups. However, a comparison of the treatment by biomarker interaction for each of the individual biomarkers (as categorized above) will still be performed. In addition, the interaction of treatment by eosinophil level, treated as a continuous variable, will be explored.
- **Association between Blood Eosinophils and *IL1RL1* Genotype:** The relationship between blood eosinophils and *IL1RL1* genotype will be evaluated graphically by displaying blood eosinophil level at visit 1 by genotype.
- **Relationship with Demographics and Disease Characteristics:** The relationship between each biomarker (blood eosinophils and *IL1RL1* genotype) and demographics and disease characteristics (including but not limited to age, sex, race, geographic region, and the number of asthma exacerbations in the 12 months prior to study entry) will be evaluated.

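### SAP 4.5.5 sets out to judge consistency across five factors but plans no estimate that compares one subgroup level with another

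*SAP*

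**What the plan says.** SAP 4.5.5 describes exploratory subgroup analyses of the exacerbation rate and of the Week 54 FEV1 change. Their purpose is "to evaluate the consistency of the primary analysis results across pre-specified subgroups". Five factors are listed: age (3 levels), sex (2), ICS dose (2), prior exacerbations (3) and region (4).

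For exacerbations, a Poisson model like the primary one "will be used for each subgroup analysis based on data subset for the patient subgroup of interest"; FEV1 is handled similarly. Estimates and 95% CIs are plotted for every dose and every level. If small subsets fail to converge, levels may be combined or stratification covariates dropped. No interaction test, interaction estimate or rule for judging consistency is given for these five factors.

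SAP 4.5.6 does plan "a comparison of the treatment by biomarker interaction for each of the individual biomarkers", meaning blood eosinophils and *IL1RL1* genotype, even though it concedes that the study was not designed for that comparison. SAP 4.5 (Type I Error Management) applies no error control to subgroup analyses.

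**The concern.** Consistency is a question about differences between levels. A CI computed inside one level says whether the effect in that level is distinguishable from none; it does not say whether the level differs from its neighbours. With 14 levels and three doses, many CIs will cross 1 and some point estimates will fall on the wrong side of 1 even when the effect is identical in everyone. The plan offers a reader of the forest plot nothing to set those results against. At stake is how an exploratory display is read, for example when choosing the population or regions of a later trial. The primary test is not at stake.

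**Working it through.** **Inputs from the documents**
- SAP 2.2: "A total of 502 patients were randomly allocated in a 1:1:1:1 ratio to receive one of three doses of MSTT1041A or placebo". The protocol plans 125 per arm, which is used below.
- SAP 2.2: rate ratio 0.6 (a 40% reduction), "assuming 0.63 exacerbations per patient per year in the placebo arm, no Poisson over dispersion, a 15% dropout rate"; α is 0.05, two-sided.
- SAP 4.5.5: 3 + 2 + 2 + 3 + 4 = 14 levels; 14 × 3 doses = 42 estimates.

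**Assumed, because the documents do not say:** the share of patients in each level, and the timing of dropout (uniform over the year).

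**Step 1. Reproduce the stated power.** Expected events are E0 = 125 × 0.63 = 78.75 on placebo and E1 = 78.75 × 0.6 = 47.25 on one dose.
- SE of the log rate ratio = √(1/78.75 + 1/47.25) = 0.184.
- Power = Φ(0.511/0.184 − 1.96) = 79.3%, matching the stated 80%.

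This loses no exposure to dropout. If the 15% who drop out contribute half a year each, average exposure is 0.925 years, the SE is 0.191 and power is 76.1%.

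**Step 2. One level, one dose.** For a level holding share s of the patients, SE = 0.191/√s. The chance of a rate ratio above 1 is Φ(−0.511/SE), and the chance that the 95% CI lies below 1 is Φ(0.511/SE − 1.96).

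| Share of patients | SE | Rate ratio above 1 | CI below 1 |
|---|---|---|---|
| 50% | 0.271 | 3% | 47% |
| 25% | 0.383 | 9% | 27% |
| 15% | 0.494 | 15% | 18% |

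**Step 3. The whole display.** The five factors classify the same patients and the three doses share one placebo arm, so the 42 estimates are correlated. The full trial was therefore simulated (5,000 to 6,000 trials per scenario) with a true ratio of 0.6 everywhere, no over-dispersion and 15% dropout. The table gives the chance of at least one rate ratio above 1.

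| Assumed shares | One dose (14) | Full display (42) |
|---|---|---|
| Equal levels | 44% | 72% |
| Moderate (smallest level 15%) | 52% | 80% |
| Skewed (smallest 10%) | 64% | 88% |
| Very skewed (smallest 7%) | 73% | 93% |

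- With no dropout: 41-69% and 68-92%.
- Covariate-adjusted subset fits, moderate shares: 53% and 82%.
- Over-dispersion of 1.5: 60-82% and 85-97%.
- Uniform 50% reduction: 23-48% and 44-75%. Uniform 30% reduction: 66-79% and 91-96%.
- About 14 of the 42 CIs exclude 1 on average (14/42 = 33%).
- A CI wholly above 1 occurs in about 2-3% of displays at most.

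**Step 4. What an interaction estimate can deliver.** For a two-level factor and one dose, the SE of the log ratio of rate ratios is SE × √(1/s + 1/(1−s)), with the overall SE between 0.184 (no exposure lost) and 0.200 (dropouts contribute nothing).
- 50/50 factor: SE 0.37-0.40, so the CI multiplies and divides the estimate by about 2.1-2.2. Power to detect a ratio of rate ratios of 0.6 is 25-28%.
- 20/80 factor: SE 0.46-0.50; power 18-20%.
- Five global tests at 5%: 1 − 0.95⁵ = 22.6% chance of at least one false flag if independent; simulation gave about 17-18%.

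**The case against.** The strongest reply is that the proposed model would change little on the plot. That is correct. In simulation, replacing subset fits with one interaction model per factor moved the chance of a stray estimate only from 54-55% to 52-53% for one dose, and from 81-83% to 79-82% for the display. A reader might infer that the missing interaction test produces the apparent reversals. It does not; small subgroups do.

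Three other stronger readings also fail.
- **Subgroups will usually look harmed.** Only point estimates stray. The plan requires 95% CIs, and these almost never lie wholly above 1. For a single dose, even the stray point estimate is close to a coin flip, and it occurs in 30-67% of trials where that dose is significant.
- **A single model sharpens the small subgroups appreciably.** Repeat runs gave a variance reduction of about 10-12% for a 15% age group and 6-7% for a 15% region, too little to be a main argument.
- **An interaction test has a far lower error rate than the display.** A per-factor 5% must not be set against a whole-display figure. The like-for-like figure is 17-23% for any of five tests.

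It is also fair to say that levels of one factor share no patients, so a reader with the subset estimates and CIs could work out an approximate ratio of rate ratios. The analyses are labelled exploratory, and the two candidate predictive biomarkers do get interaction analyses. These points lower the priority. They do not explain why a section whose stated aim is consistency leaves the comparison to the reader, when 4.5.6 makes the same kind of comparison despite admitted low power.

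**Conclusion.** The gap is real and confined to SAP 4.5.5: five factors, 42 plotted estimates, an aim of consistency, and no planned quantity that measures it. Under the plan's own assumptions and a perfectly uniform effect, roughly 70-95% of displays would show at least one rate ratio above 1 (roughly 40-75% for one dose), and about two thirds of the CIs would include 1. Those ranges depend on assumed subgroup shares and on the 40% reduction. They rise with over-dispersion or a smaller effect and fall with a larger one. An interaction estimate gives readers the right comparison, but an imprecise one. This is a low-priority improvement to an exploratory analysis and leaves the primary conclusion untouched.

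**What to change.** Add to SAP 4.5.5, before the Week 54 analysis (SAP Section 1 bars later changes):

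1. For each of the five factors, fit one Poisson model on all mITT patients with the primary covariates, the factor as split in 4.5.5, and treatment-by-subgroup terms. Age, sex and the three-level history split need their own main effects, because the primary covariates lack them.
2. On the forest plot, print the ratio of rate ratios with 95% CI for each dose, against a reference level named in advance, and one global interaction p-value per factor.
3. For FEV1, report the Week 54 difference in treatment effect between levels with its CI. Because levels are disjoint, it can be formed from the subset estimates with SE = √(SE₁² + SE₂²), which avoids a three-way repeated-measures model.
4. State that consistency is judged from the interaction estimates and CIs, not from whether a subset's CI crosses 1; that a non-significant interaction is not evidence of consistency (power about 18-28% for a ratio of rate ratios of 0.6); and that five tests carry about a 17-23% chance of at least one false flag.

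The cost is SAP wording and five further exacerbation models; no new data are needed. The downsides are that covariate effects are assumed common across levels, and that interaction power is low.

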4.5.6 Biomarker Analyses

Additional biomarker analyses will be performed to further evaluate the treatment benefit by biomarker-defined patient subpopulations. Two biomarkers will be considered individually: blood eosinophils and *IL1RL1* genotype.

Based on the primary efficacy endpoint (incidence of asthma exacerbations) and the secondary efficacy endpoint (absolute change in pre-bronchodilator FEV₁ from the randomization visit at Week 54), the treatment benefit will be assessed for the following pre-specified biomarker-defined patient subpopulations:

- **Blood eosinophil level at visit 1:** Eosinophil-high will be defined as ≥ 300 cells/ μ L and eosinophil-low will be defined as < 300 cells/ μ L at visit 1. It is estimated that approximately 25% of enrolled patients will be classified as eosinophil-high.
- ***IL1RL1* genotype:** Patient subsets will be defined by *IL1RL1* genotype, using the Single Nucleotide Polymorphisms (SNP) at rs10206753. Genotype-positive will be defined as those patients who are homozygous for the common variant (i.e., TT). Genotype-negative will be defined as patients who are not homozygous for the common variant (i.e., CT or CC). It is estimated that approximately 50% of enrolled patients will be classified as genotype-positive.

For the primary efficacy endpoint, a Poisson regression model similar to that specified for the primary analysis (Section 4.5.1) will be used for each subgroup analysis based on data subset for the biomarker subgroup of interest. Baseline covariates included in the primary analysis but no longer relevant given the subgroup of interest will be excluded from the model. A similar approach will be used for the secondary efficacy endpoint based on FEV₁. Point estimates for the treatment benefit (MSTT1041A vs. placebo) within each biomarker patient group as defined above will be presented along with 95% CIs and p-values.

Similarly, the appropriateness of the chosen cutoff values to define the biomarker-high/genotype-positive versus biomarker-low/genotype-negative patient group

for the primary analysis (e.g., 300 cells/ μL for eosinophils) will be assessed by performing additional analyses for the primary efficacy endpoint (incidence of asthma exacerbations) and the secondary efficacy endpoint (absolute change in pre-bronchodilator FEV₁ from randomization at Week 54) with the use of pre-specified alternative subgroups:

- **Alternative Subgroups for Blood Eosinophils:** Patients will be categorized into blood eosinophil subgroups defined as ≥ 150 cells/ μL and < 150 cells/ μL at visit 1.
- **Alternative Subgroups for *IL1RL1* Genotype:** Patients will be categorized into one of three genotype subgroups: TT, CT, or CC.

Covariate adjustment for these analyses will follow the principles as described in Section 4.5. All other elements of the analysis will remain the same as in the primary analysis. If convergence problems with the statistical models arise due to a small number of patients per subgroup, the analysis may be simplified by excluding baseline stratification variables from the model. Point estimates for the treatment benefit (MSTT1041A vs. placebo) within each biomarker patient subgroup will be presented as defined above, along with associated 95% CIs and p-values.

Additional exploratory analyses that will be performed include:

- **Prognostic Effect:** The prognostic effect of blood eosinophils and *IL1RL1* genotype will be evaluated by assessing the relationship between baseline biomarker levels and the observed rate of protocol-defined exacerbations based on patients who received treatment with placebo.
- **Treatment by Biomarker Interaction:** This study was not designed to compare the reduction in asthma exacerbation rate associated with MSTT1041A treatment between the biomarker-high/genotype-positive and the biomarker-low/genotype-negative patient groups. However, a comparison of the treatment by biomarker interaction for each of the individual biomarkers (as categorized above) will still be performed. In addition, the interaction of treatment by eosinophil level, treated as a continuous variable, will be explored.
- **Association between Blood Eosinophils and *IL1RL1* Genotype:** The relationship between blood eosinophils and *IL1RL1* genotype will be evaluated graphically by displaying blood eosinophil level at visit 1 by genotype.
- **Relationship with Demographics and Disease Characteristics:** The relationship between each biomarker (blood eosinophils and *IL1RL1* genotype) and demographics and disease characteristics (including but not limited to age, sex, race, geographic region, and the number of asthma exacerbations in the 12 months prior to study entry) will be evaluated.

